- 10. Triplicate 12-leads electrocardiogram (ECG): Triplicate ECGs will be collected at times specified in the Schedule of Activities. At each time point, at least a 10 second strip, three consecutive 12-lead ECGs will be performed 1-5 minutes apart to determine mean QTcF interval. The Screening ECG will be a single, 12-lead ECG. ECGs on Day 1 of each Cycle will be collected prior to dosing, and at the end of infusion (approximately 1 hour) following administration of each dose of PF-04518600. Additional ECGs will be collected on Cycle 1 Day 2 (C1D2), Cycle 1 Day 8 (C1D8), Cycle 2 Day 8 (C2D8), and Cycle 3 Day 8 (C3D8). When coinciding with blood sample draws for pharmacokinetics (PK), ECG assessment should preferably be performed prior to blood sample collection, such that the blood sample is collected at the nominal time. All ECGs will be reviewed by a centralized ECG vendor. If the mean QTcF is prolonged (value of >500 msec), the ECGs should be reevaluated by a qualified person at the institution for confirmation. Additional triplicate ECGs may be performed as clinically indicated. Refer to Section 7.1.5 (12-Lead) ECG for further details.
- 11. Hematology: complete blood count (CBC) to include hematocrit, hemoglobin, platelets, white blood cells (WBC), absolute neutrophils, lymphocytes, monocytes, eosinophils, and basophils. Assessments conducted on Cycle 1 Day 1 (C1D1) must be completed within 48 hours prior to dosing. If screening assessments are performed within 72 hours prior to C1D1, there is no need to repeat assessments on C1D1. Assessments performed on Cycle 2 Day 1 (C2D1) and Day 1 of each subsequent cycle should be performed within 48 hours prior to dosing. See Assessments Section 7.1.3 for Laboratory Tests list.

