### **5.4.5.5. Dose Delay**

Re-treatment following treatment interruption for treatment related toxicity or at the start of any new cycle may not occur until all of the following parameters have been met:

- ANC  $\ge 1,000/\text{mm}^3$ .
- Platelets count ≥50,000/mm³. HCC only: based on investigator judgment, after consultation with sponsor's medical monitor, change from baseline will be considered, and levels of ≥25,000/mm³ may be acceptable.
- Non-hematologic toxicities have returned to baseline or Grade ≤1 severity (or, at the investigator discretion, Grade ≤2 if not considered a safety risk for the patient).

If a treatment delay results from worsening of hematologic or biochemical parameters, the frequency of relevant blood tests should be increased as clinically indicated. Patients experiencing Grade 3 or 4 potentially treatment related toxicity or intolerable Grade 2 toxicity despite supportive care should have their treatment interrupted/delayed. Appropriate follow-up assessments should be done until adequate recovery (or until deemed irreversible) occurs as assessed by the Investigator.

If these conditions are met within 2 weeks of treatment interruption or cycle delay, PF-04518600 or PF-04518600/utomilumab may be resumed. For monotherapy, please refer to Section 5.4.5.6.1 (Dose Reductions, Interruptions and Discontinuation Part A Monotherapy) for adverse events requiring dose reduction at the time of treatment resumption. For combination therapy, intrapatient dose reduction will not be permitted (see Section 5.4.5.6.2 Dose Reductions, Interruptions and Discontinuation Part B Combination Therapy).

If these conditions are not met, treatment resumption must be delayed up to a maximum of 4 weeks. If these parameters have not been met after 4 weeks of dose interruption or 4 weeks of new cycle delay, permanent discontinuation of treatment with PF-04518600 or PF-04518600/utomilumab should be considered. Treatment resumption for patients

recovering from treatment-related toxicity after 4 weeks of treatment interruption or cycle delay can be considered only if the patient is deemed to be deriving obvious clinical benefit per the investigator's best medical judgment and needs to be agreed between the investigator and the sponsor.

If a treatment interruption continues beyond Day 14 of the current cycle, then the day when treatment is restarted will be counted as Day 1 of the next cycle.

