# 5.4.5.6.2. Part B Combination Therapy

Intrapatient dose reductions are not permitted during the combination therapy with PF-04518600 and utomilumab unless, in discussion with the sponsor, a dose combination level is deemed to be above the determined MTD for the combination.

Given the expected similarities of side effect profile and mechanism between the two co-stimulation monoclonal antibodies, both treatments must be interrupted or discontinued together. Patients will not be permitted to continue treatment with one agent, while the other agent is either interrupted or permanently discontinued. If infusion related reactions are observed following the administration of the first agent, administration of the second agent will be withheld until symptoms resolve (see Section 5.4.5.1 Infusion Reactions).

Treatment of irAEs should follow guidelines set forth in Table 4 in Section 5.4.5.4 Recommended dose modifications for any other drug-related toxicity are illustrated in Table 6.

Table 6. Treatment Interruptions/ Discontinuations for Drug Related Toxicity at Start of Subsequent Cycle

Toxicity	NCI CTCAE Severity Grade	Treatment Modifications
Hematologic abnormalities.	Grade 3	
 
Withhold until recovery to Grade 1 or better.
 
If toxicity does not resolve to Grade 1 or better within 4 weeks of last infusion, consider permanent discontinuation after consultation with the sponsor.
 
Upon the second occurrence of the same Grade 3 toxicity that does not resolve to Grade ≤1 by the next administration, treatment must be permanently discontinued.
 

	Grade 4	Permanent discontinuation.     Exceptions are:     Single laboratory values out of normal range that are unlikely related to investigational product (s) as assessed by the Investigator, do not have any clinical correlate, and resolve within 7 days with adequate medical management.
Infusion-related reaction.	Grade 1-4	• See Section 5.4.5.1 and Appendix 4.
Hypersensitivity reaction.	Grade 1-4	• See Section 5.4.5.2 and Appendix 4.

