Other non-hematologic toxicities and laboratory abnormalities.	Grade 2	
 
If toxicity resolves to Grade ≤1 by the next administration, treatment may continue.
 
If toxicity does not resolve to Grade ≤1 by the next administration despite optimal treatment, the next infusion should be omitted. If at the end of 4 weeks of dose holding, the event has not resolved to Grade ≤1, the patient should permanently discontinue treatment (except for hormone deficiencies that can be managed by replacement therapy and for which up to 2 additional subsequent doses may be omitted).
 

Table 6. Treatment Interruptions/ Discontinuations for Drug Related Toxicity at Start of Subsequent Cycle

Toxicity	NCI CTCAE Severity Grade	Treatment Modifications
	Grade 3	Permanent discontinuation, Exceptions are:
		
 
Transient (≤6 hours) flu-like symptoms or fever, which is controlled with medical management.
 
Transient (≤24 hours) fatigue, local reactions, headache that resolves to Grade ≤1.
 
Nausea and vomiting controlled by medical therapy.
 
Diarrhea, skin toxicity, or liver function test (ALT, AST, or Gamma-glutamyltransferase [GGT]) that resolves to ≤ Grade 1 in less than 7 days after medical management (eg, immunosuppressant treatment) has been initiated.
 
Amylase or lipase abnormality that is not associated with symptoms or clinical manifestations of pancreatitis.
 
Tumor flares phenomenon defined as local pain, irritation, or rash localized at sites of known or suspected tumor.
 
Non hematologic laboratory abnormality that do not require medical intervention or hospitalization.
 
Single non hematologic laboratory values out of normal range that are unlikely related to treatment as assessed by the Investigator, do not have any clinical correlate, and resolve to ≤ Grade 1 within 7 days with adequate medical management.
 

	Grade 4	Permanent discontinuation, Exceptions are:
		
 
Non hematologic laboratory abnormality that does not require medical intervention or hospitalization. Single non hematologic laboratory values out of normal range that are unlikely related to treatment as assessed by the Investigator, do not have any clinical correlate, and resolve within 7 days with adequate medical management.
 
Amylase or lipase abnormality that is not associated with symptoms or clinical manifestations of pancreatitis.
 

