# 7.1.5. (12-Lead) Electrocardiogram

Electrocardiogram (ECG): A single 12-lead (with at least a 10-second rhythm strip) tracing will be used for the screening ECG. Triplicate 12-lead (with at least a 10-second rhythm strip) tracing will be used for all other scheduled ECGs. Unscheduled visits do not require triplicate ECGs. It is preferable that the machine used has a capacity to calculate the

standard intervals automatically. All 12-lead ECGs will be reviewed by a central laboratory. At each time point (see the Schedule of Activities) three consecutive ECGs will be performed at approximately 1-5 minutes apart to determine the mean QTcF interval. Fridericia's formula (QTcF) is calculated as follows:

$$QTcF = QT / (RR)^{0.33}$$

If the mean QTcF is prolonged (>501 msec, ie, ≥ CTC AE Grade 3), then the ECGs should be re-evaluated by a qualified person at the site for confirmation as soon as the finding is made, including verification that the machine reading is accurate. If manual reading verifies a QTcF of >501 msec, immediate correction for reversible causes (including electrolyte abnormalities, hypoxia and concomitant medications for drugs with the potential to prolong the QTcF interval) should be performed. In addition, repeat ECGs should be immediately performed hourly for at least 3 hours until the QTcF interval falls below 501 msec. If QTcF interval reverts to less than 501 msec, and in the judgment of the investigator(s) and sponsor is determined to be due to cause(s) other than investigational product, treatment may be continued with regular ECG monitoring. If in that timeframe the QTcF intervals rise above 501 msec the investigational product will be held until the QTcF interval decreases to 480 msec. Patients will then re-start the investigational product at the next lowest dose level. If the QTcF interval has still not decreased to 480 msec after 2-weeks, or if at any time a patient has a QTcF interval >515 msec or becomes symptomatic, the patient will be removed from study drug. Additional triplicate ECGs may be performed as clinically indicated.

Prior to concluding that an episode of prolongation of the QTcF interval is due to investigational product, thorough consideration should be given to potential precipitating factors (eg, change in patient clinical condition, effect of concurrent medication, electrolyte disturbance) and possible evaluation by specialist.

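### Section 7.1.5 restarts patients held for QTcF above 501 msec one dose level lower in every study part, although Part B forbids intrapatient dose reduction

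*Protocol*

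**What the plan says.** **The ECG rule.** Section 7.1.5 opens its action rule with "If the mean QTcF is prolonged (>501 msec, ie, ≥ CTC AE Grade 3", so the protocol itself grades the trigger as Grade 3 or higher. After manual verification, reversible causes are corrected and hourly ECGs follow for at least 3 hours. If QTcF rises above 501 msec in that window, treatment is held until it comes down to 480 msec. Then: "Patients will then re-start the investigational product at the next lowest dose level". A patient who exceeds 515 msec, has symptoms, or has not reached 480 msec after 2 weeks comes off study drug.

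**Where it applies.** Footnote 10 of the Part B1 schedule and footnote 10 of the shared A2/B2 schedule both say "Refer to Section 7.1.5 (12-Lead) ECG for further details".

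**The Part B dosing rules.** Section 5.4.5.6.2 says "Intrapatient dose reductions are not permitted during the combination therapy with PF-04518600 and utomilumab unless", the one exception being a combination level deemed above the MTD in discussion with the sponsor. It adds that "both treatments must be interrupted or discontinued together". On resumption after an interruption, Section 5.4.5.5 says "For combination therapy, intrapatient dose reduction will not be permitted". For toxicity other than immune-related events, Section 5.4.5.6.2 states "Recommended dose modifications for any other drug-related toxicity are illustrated in Table 6". In that table the Grade 3 and Grade 4 entries for other non-hematologic toxicity both begin "Permanent discontinuation, Exceptions are".

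**The concern.** The restart sentence is an instruction, not an option. It is the most specific text in the protocol on QTcF, and it reaches Part B patients through the schedules. A site that follows it would re-expose a Part B patient to reduced treatment after a Grade 3 or higher cardiac finding, which the Part B section forbids. If the event is drug-related, the Part B table would instead take the patient off both agents. What is at stake is the consistency of a safety action across sites. Inference on the trial's endpoints is not at stake.

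**Working it through.** No power or error-rate calculation applies, and the plan states no figure to reproduce. The check follows one patient through each text and then counts the patients covered.

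**The patient.** In Part B, with verified QTcF above 501 msec that rises above 501 msec again in the repeat window, never exceeds 515 msec, causes no symptoms, and falls to 480 msec within 2 weeks.

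| Text | Instruction for this patient |
|---|---|
| Section 7.1.5 | Restart one dose level lower |
| Protocol Summary (Part B1), Sections 5.4.5.5 and 5.4.5.6.2 | No intrapatient reduction, unless the combination level is deemed above the MTD |
| Table 6, if drug-related | Permanent discontinuation, unless a listed exception applies |

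**Conflict 1, whatever the cause.** Neither the hold-and-restart sentence nor the Part B ban depends on relatedness, so rows 1 and 2 are incompatible. The above-MTD exception does not reconcile them: it concerns a combination level, one patient's QTcF event does not establish it, and Section 7.1.5 does not mention it.

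**Conflict 2, drug-related events only.** Table 6 lists 8 exceptions for Grade 3 and 3 for Grade 4 other non-hematologic toxicity. Of these 8 + 3 = 11, none names an ECG or QTc finding. The nearest covers laboratory abnormalities needing no medical intervention. Section 7.1 lists ECGs separately from laboratory assessments, the laboratory table in Section 7.1.3 has no ECG interval, and Section 7.1.5 requires reversible causes to be corrected at once. The exception for single values unlikely to be treatment-related cannot apply to a drug-related event.

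**The step-down is also undefined in Part B.** Under Section 3.1.2.1, combination levels move by changing either agent or both, and Section 7.1.5 does not say which to lower. Part B2 has one selected pair, 30 mg PF-04518600 with 20 mg utomilumab.

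**Part A has no such conflict.** Table 5 also holds for Grade 3 or 4 related non-hematologic toxicity and then reduces by one level. The only pointer from the dose-modification rules to ECG events is the note after Table 5. It cites Section 9.6.3, which covers ECG analysis and contains no dosing action. The restart sentence may therefore have been written for monotherapy, but nothing in Section 7.1.5 says so and no rule states which section prevails.

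**Patients covered.**
- Part B1: about 55 (Protocol) or 53 (SAP Section 2.1)
- Part B2: up to 2 × 20 = 40
- Study maximum: about 210
- 55 + 40 = 95; 95/210 = 45%
- 53 + 40 = 93; 93/210 = 44%

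**The case against.** The strongest reply is that Part B already answers the question. Section 5.4.5.5 governs resumption in both parts, and for combination therapy it repeats the ban. Section 5.4.5.6.2 and the Protocol Summary say the same, and the B1 and B2 administration sections cite 5.4.5.6.2. Three explicit prohibitions stand against one general sentence in an assessments section, so many sites would reach the right answer. That reduces the practical risk. It leaves the contradiction in place, because no text gives precedence and Section 7.1.5 is the more specific rule for QTcF.

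A second reply is that Table 6 is presented as recommended, is titled for the start of a subsequent cycle, and sits beside Section 5.4.5.5, which has Grade 3 or 4 potentially related toxicity interrupted and allows resumption on recovery. The word recommended does make the ban the firmer of the two conflicts. But a restart after a hold is the setting the table's title describes, and Section 5.4.5.5 refers combination patients to 5.4.5.6.2. Neither text permits a reduced-dose restart.

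Third, the harm is bounded. Entry generally excludes QTcF above 470 msec, and Section 7.1.5 removes anyone above 515 msec, with symptoms, or not recovered in 2 weeks. This stands. So does the point that Amendment 6 reports the B2 dose as already chosen from B1 results, so new enrollment under the text is mainly the up to 40 patients in B2 (40/210 = 19%), plus any B1 patients still on treatment, a number the documents do not give.

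**Conclusion.** The concern holds. As written, Section 7.1.5 is wrong for Part B: its reduced-dose restart contradicts the ban on intrapatient reduction for any such hold, and contradicts Table 6 when the event is drug-related. The text covers 95 of about 210 planned patients (45%), or 93 (44%) on the SAP's count. That is the reach of the text over full planned enrollment and says nothing about how often the path would occur. The path is rare and no rate can be estimated from the documents. The conclusion rests on reading the unrestricted sentence, with the schedule footnotes, as applying to Part B, and on an ECG interval not being a laboratory abnormality for Table 6. Only the second conflict needs the latter. Part B already contains a protective instruction for drug-related events, and the DLT rule, sample size and analyses are untouched. It should be corrected because it directs re-dosing after a Grade 3 or higher cardiac finding.

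**What to change.** In Section 7.1.5, limit the restart at the next lowest dose level to Part A. Add one sentence for Part B: drug-related QTcF prolongation of Grade 3 or higher follows Table 6, both agents are stopped together, and the dose is not reduced, with the above-MTD exception in Section 5.4.5.6.2 unchanged.

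Two small clarifications belong in the same edit. State the Part B action for a hold judged unrelated to drug; holding both agents and resuming without reduction would fit the existing rules. Redirect the note after Table 5 from Section 9.6.3 to Section 7.1.5.

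The cost is protocol wording: two sentences for the main correction and two minor edits, with the IRB/EC approval that Section 12.1 requires for an amendment. No assessment, patient number or analysis changes.

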# 7.1.6. Echocardiogram or Multigated Acquisition (MUGA) Scan

Echocardiogram or multigated acquisition (MUGA) will be evaluated in patients with previous history of anthracycline treatment. For these patients, an echocardiogram or MUGA will be performed at screening and every 3 months whilst on treatment and when clinically indicated. An echocardiogram or MUGA will be performed at the end of treatment (EOT) visit if not performed within 3 months of discontinuation. The following parameters will be evaluated: ventricular function (including left ventricular ejection fraction [LVEF], end systolic volume [ESV] and end diastolic volume [EDV]), qualitative evaluation of chamber size, and wall motion. A Doppler examination will be completed and should include an assessment of mitral valve, atria, right ventricle, tricuspid valve, aortic valve, pulmonic valve, great vessels, and pericardium.

#### 7.2. Pharmacokinetics Assessments

# 7.2.1. Blood for PK Analysis of PF-04518600 and Utomilumab

For both Part A Monotherapy and Part B Combination Therapy, blood samples for the analysis of PF-04518600 concentrations will be collected into appropriately labeled tubes at times specified in the Schedule of Activities of the protocol. For each analysis, 5 mL of blood samples will be collected to provide approximately 2 mL serum. The PK sampling schedule may be modified based on emerging PK data.

For Part B Combination Therapy only, blood samples (2 mL whole blood at each time point) will be collected to provide serum for PK analysis of utomilumab as outlined in the Schedule of Activities. The PK sampling schedule may be modified based on emerging PK data.

The 1 hr samples should be collected immediately before the infusion ends for the corresponding investigational agent from the contra-lateral arm of the infusion.

In addition to samples collected at the scheduled times, an additional blood sample should be collected from patients experiencing unexpected and/or serious AEs and the date and time of blood sample collection and of last dosing prior to PK collection documented in the CRF.

Where noted in the Schedule of Activities, blood samples for PF-04518600 (both Part A and Part B) and utomilumab (Part B only) concentrations will be collected at approximately the same time as pharmacodynamic samples whenever possible.

All efforts will be made to obtain the pharmacokinetic samples at the exact nominal time relative to dosing. However, the exact time of the sample collection will always be noted on the CRF. Samples obtained within 10% of the nominal time (eg, within 6 minutes of a 60 minute sample) from dosing will be not be captured as a protocol deviation. If a scheduled blood sample collection cannot be completed for any reason, the missed sample time may be re-scheduled with agreement of clinical investigators, patient and Sponsor. Additional instructions for sample collection, processing, storage and shipping will be provided in the lab manual.

PK samples will be assayed for PF-04518600 (both Part A and Part B) and utomilumab (Part B only) using validated analytical methods in compliance with Pfizer standard operating procedures. Details regarding the collection, processing, storage and shipping of the blood samples will be provided in the study manual.

# 7.4. Tumor Response Assessments

Tumor assessments will include all known or suspected disease sites. Imaging may include chest, abdomen and pelvis computed tomography (CT) or magnetic resonance imaging (MRI) scans; brain CT or MRI scan for patients with known or suspected brain metastases; bone scan and/or bone X-rays for patients with known or suspected bone metastases.

The same imaging technique used to characterize each identified and reported lesion at baseline will be employed in the subsequent tumor assessments.

Anti-tumor clinical activity will be assessed through radiological tumor assessments conducted at baseline, during treatment as specified in the applicable Schedule of Activity, whenever disease progression is suspected (eg, symptomatic deterioration), until confirmed progressive disease or start of subsequent anticancer therapy whichever comes first.

Assessment of tumor response will be made using RECIST version 1.1 (Appendix 5) and irRECIST response criteria (Appendix 6). 86,87

All patients' files and radiologic images must be available for source verification and for potential peer review.

# 7.6. Immunogenicity Evaluations

Bioanalysis to assess for anti-drug (PF-04518600 or utomilumab) antibodies (ADA) will be performed. All samples that are positive in a screening assay will be further characterized in terms of antibody specificity. A tiered approach to screening, confirmation and titer/quantitation will be utilized. The screening assay with competitive confirmatory steps followed by the titer assay will be used. Samples may also be analyzed in neutralization assays (NAb). Patients having an unresolved adverse event that is possibly related to ADA formation will be asked to return for ADA and drug concentration blood sampling at approximately 3 month intervals until the adverse event or its sequelae resolve or stabilize at

a level acceptable to the investigator, and sponsor concurs with that the investigator's assessment, up to 6 months from the EOT or the day of early withdrawal.

Blood samples (10 mL) to provide approximately 5 mL of serum for ADA and NAb analysis will be collected into appropriately labeled tubes at times specified in the Schedule of Activities of this protocol.

Additional instructions for sample collection, processing, storage, and shipping will be provided in the lab manual.

Samples will be analyzed using a validated analytical method in compliance with Pfizer standard operating procedures.

As part of understanding the immunogenicity of the investigational product, samples may be used for additional characterization of an observed immunogenicity response and/or evaluation of the bioanalytical method. These data will be used for internal exploratory purposes and will not be included in the clinical report. Samples collected for this purpose will be retained in accordance to local regulations and if not used within this timeframe, will be destroyed.

